8.2.6 Bone Marrow Aspirate

A BMA, for response assessments and research, will be obtained as indicated in Table 1-1 and Table 1-2.

8.3 Safety Assessments

8.3.1 Clinical Laboratory Assessments

A list of testing to be performed on the blood and urine samples is provided in (Appendix E). All laboratory safety data will be reviewed by the Investigator or designee for clinical significance as defined by an applicable list of normal values on file (i.e., local or central, as applicable).

Additional laboratory samples may be taken at the discretion of the Investigator or designee (e.g., if the results of any tests fall outside reference ranges or if clinical symptoms necessitate testing to ensure patient safety).

8.3.2 Physical Examination

Full and symptom-directed physical examinations will be performed according to the schedule in Table 1-1, and Table 1-2. Full physical examinations, assessing the patient's overall health and physical condition, will consist of the following body systems: eyes, ears, nose, throat, lymph nodes, dermatologic, cardiovascular, respiratory, gastrointestinal, musculoskeletal, and nervous systems.

8.3.3 Hematology

Hematology assessments will be performed according to the schedule in Table 1-1 and Table 1-2. A list of hematology tests to be performed is provided (Appendix E).

8.3.4 Hemoglobin Electrophoresis

A hemoglobin electrophoresis will be performed locally according to the schedule in Table 1-1.

8.3.5 Coagulation Parameters

Coagulation parameters assessments will be performed according to the schedule in Table 1-1 and Table 1-2. A list of coagulation parameters tests to be performed is provided (Appendix E).

Version 3.0; 31 July 2023

8.3.6 Serum Chemistry

Chemistry assessments will be performed according to the schedule in Table 1-1 and Table 1-2. A list of serum chemistry tests to be performed is provided (Appendix E).

8.3.7 Urinalysis

Urinalysis will include assessment of color, appearance, and by urine dipstick according to the schedule in Table 1-1 and Table 1-2. Microscopic analysis (RBCs, white blood cells [WBCs], microalbumin, bacteria and casts) may be performed as clinically indicated. A list of the tests to be performed is provided (Appendix E).

8.3.8 12-Lead Electrocardiogram

12-Lead ECGs will be performed according to the schedule in Table 1-1 and Table 1-2. Electrocardiograms (ECGs) (12-lead) should be recorded in triplicate after a patient has rested for at least 5 minutes in the supine position. All Triplicate ECGs will be taken one minute apart or with the three ECGs collected within about a five-minute window.

If the scheduled time for a safety ECG coincides with a blood collection, the safety ECG should be performed prior to the blood collection. The same timing for obtaining safety ECGs (ie, prior to blood collection) should be used for all safety ECG measurements. If the ECG cannot be performed prior to blood collection, the ECG should be done after a sufficient rest period of at least 15 minutes to minimize interference with ECG measurements.

8.3.9 Pregnancy

A serum pregnancy test for the presence of β -human chorionic gonadotropin (β -HCG) will be performed during Screening for all female participants of childbearing potential.

During active study participation, pregnancy tests will be urine pregnancy tests and will be performed locally if indicated.

If a urine pregnancy test is positive, study treatment must be held until the results are confirmed with a serum pregnancy test, and permanently discontinued if confirmed positive. Results of all pregnancy tests will be reported and must be negative prior to study continuation and/or dosing (see also Section 8.7.4).

8.3.10 Concomitant Medications and Procedures

All medications received by the patient while in the study as described in Section 6.7.1, or any procedures that the patient has undergone will be recorded according the Schedule of Events (Table 1-1, Table 1-2).

8.4 Pharmacokinetic Sampling

Venous blood samples will be collected to characterize the PK of etavopivat. Samples will be collected, processed, and shipped according to a lab manual provided by the Sponsor and/or bioanalytical laboratory.

Version 3.0; 31 July 2023

8.5 Pharmacodynamic Sampling

Pharmacodynamic analysis will include measurement of 2,3-DPG and ATP and will be conducted as indicated in Table 1-1 and Table 1-2.

8.6 Exploratory Laboratory Assessments

Exploratory laboratory samples will be collected according to the Schedule of Events (Table 1-1 and Table 1-2).

Samples obtained will include BMA to evaluate bone marrow progenitors by cell colony assays and terminal erythroid differentiation by flow cytometric analysis. BMA and peripheral blood will be obtained for cancer-associated mutations and/or genetic alterations.

Serum will be obtained to evaluate markers of ineffective erythropoiesis and iron metabolism, including but not limited to erythropoietin, soluble transferrin receptor, iron, total iron binding capacity (including transferrin saturation), erythroferrone, and hepcidin.

Refer to the study laboratory manual for additional details on processing, storage, and shipment of exploratory laboratory samples where indicated.

8.7 Adverse Events, Serious Adverse Events, and Other Safety Reporting

8.7.1 Definition of an Adverse Event

An AE is defined as any untoward medical occurrence in a patient administered a medicinal product that does not necessarily have a causal relationship with this treatment.

An AE can, therefore, be any unfavorable and unintended sign (including an abnormal laboratory finding), symptom, or disease temporally associated with the use of an investigational product, whether or not the AE is related to the investigational medicinal product.

This includes an exacerbation of pre-existing conditions or events, intercurrent illnesses, drug interaction, or the significant worsening of the indication under investigation that is not recorded elsewhere on the eCRF under specific efficacy assessments.

Anticipated fluctuations of pre-existing conditions that do not represent a clinically significant exacerbation or worsening are not considered AEs.

It is the responsibility of the Investigator to document all AEs that occur during the study (from time of the first dose of study drug through 28 days after the last dose of study drug). AEs should be elicited by asking the patient a non-leading question (eg, "Have you experienced any new or changed symptoms since we last asked/since your last visit?"). The existence of an AE may be concluded from a spontaneous report of the patient; from the physical examination; or from special tests such as the ECG, laboratory assessments, or other study-specified procedure (source of AE).

8.7.2 Serious Adverse Events

8.7.2.1 Definition

An SAE is any untoward medical occurrence that occurs at any dose that:

- Results in death. Any event resulting in death during the reporting period [from time of the first dose of study drug through 28 days after last dose of study drug] must be treated as an SAE and reported as such.
- Is life-threatening (patient is at immediate risk of death from the event as it occurred) NOTE: this is different than life-threatening severity criteria.
- Requires in-patient hospitalization (formal admission to a hospital for medical reasons) or prolongation of existing hospitalization. NOTE: visits to Emergency Rooms, Urgent Care, Accident/Emergency Units, or visits resulting in brief care under, 'Observation Status', do not meet the criteria of in-patient hospitalization.
- Results in persistent or significant disability/incapacity
- Results in a congenital anomaly/birth defect
- Important medical events that may not result in death, are not life-threatening, or do not require hospitalization may be considered SAEs when, based on appropriate medical judgment, they may jeopardize the patient and may require medical or surgical intervention to prevent one of the outcomes listed in this definition.

The following must be reported as an SAE using the important medical event criterion if no other seriousness criteria are applicable:

- Suspicion of transmission of infectious agents via IMP
- Risk of liver injury defined as alanine aminotransferase (ALT) or aspartate aminotransferase (AST) > 3x ULN and total bilirubin > 2x ULN where no alternative aetiology exists (Hy's law)

8.7.2.2 Events or Outcomes Not Qualifying as Serious Adverse Events

The following are not considered SAEs and therefore do not need to be reported as such:

• Pre-planned procedures (planned prior to signing of ICF) or elective hospitalization such as social and/or convenience situations (e.g., hospitalization due to weather or travel issues)

Overdose of either study drug or concomitant medication unless the event meets SAE criteria (e.g., hospitalization). However, the event should still be captured as described in Section 8.7.11.

8.7.3 Clinical Laboratory Assessments as Adverse Events

It is the responsibility of the Investigator to assess the clinical significance of all abnormal values as defined by the applicable list of reference ranges from the laboratory (i.e., local or central, as applicable). In some cases, significant changes in lab values within the normal range will require similar judgment.

An abnormal laboratory value that is not already associated with an AE is to be recorded as an AE only if any one of the following criteria is met:

- An action on the study drug is made as a result of the abnormality
- Intervention for management of the abnormality is required
- At the discretion of the Investigator should the abnormality be deemed clinically significant

51 of 77

8.7.4 Pregnancy or Drug Exposure during Pregnancy

If a patient becomes pregnant during the study the Investigator is to stop dosing with study drug immediately. A pregnancy is not considered to be an AE or SAE; however, it must be reported to the Sponsor using the Pregnancy Report Form within the same timelines as an SAE. This applies to a female patient or the female partner of a male patient. The pregnancy should be followed through to outcome, whenever possible. Once the outcome of the pregnancy is known, the Pregnancy Outcome Reporting Form should be completed and reported to the Sponsor. AEs or SAEs that occur during pregnancy will be assessed and processed according to the AE or SAE processes using the appropriate AE or SAE forms. Should the outcome of pregnancy meet SAE criteria (for example, spontaneous abortion, congenital anomaly, stillbirth, etc.), that should be reported as an SAE accordingly.

8.7.5 Procedures for Recording and Reporting Adverse Events and Serious Adverse Events

Any AE or SAE that occurs from time of the first dose of study drug through 28 days after the last dose of study drug should be recorded on the AE eCRF. Only SAEs that occur from the time of consent until first dose of study drug that are considered to be related to a protocol-mandated procedure need to be reported as an SAE. All other AEs and SAEs from time of consent until first dose of study drug should be reported as medical history.

In order to avoid vague, ambiguous, or colloquial expressions, the AE should be recorded in standard medical terminology rather than the patient's own words. Whenever possible, the Investigator should combine signs and symptoms that constitute a single disease entity or syndrome into a final diagnosis, if appropriate. For example, fever, cough, and shortness of breath may be reported as pneumonia, if that is the final diagnosis. Each AE is to be evaluated for duration, severity, seriousness, and causal relationship to the investigational drug. The action taken and the outcome must also be recorded.

Serious Adverse Events: SAEs that occur during Screening and are related to a protocol-mandated procedure or SAEs that occur from first dose to within 28 days after last dose of study drug, whether or not related to study drug, must be reported to Novo Nordisk Global Safety within 24 hours of knowledge of the event (see Page 4). After the 28-day reporting window, only SAEs assessed as related to study drug need to be reported. All SAEs, regardless of relationship to study drug, must be reported using the Novo Nordisk SAE Report Form. It is important that the Investigator provides an assessment of relationship of the SAE to study treatment at the time of the initial report. The contact information for reporting of SAEs can be found on the Novo Nordisk SAE Report Form itself and is also provided on Page 4.

8.7.6 Grading the Severity of Adverse Events

The severity of the AE will be graded according to the CTCAE grading scale (Grades 1-5), per CTCAE v5. Should criteria not be available for a specific event term, the definitions noted below may be used:

- Grade 1 (Mild): event is usually transient and does not interfere with the patient's daily activities
- Grade 2 (Moderate): event introduces a low level of inconvenience or concern to the patient and may interfere with daily activities

- Grade 3 (Severe): event interrupts the patient's usual daily activities and hospitalization (or prolongation of hospitalization) may be required
- Grade 4 (Life-threatening): event requires urgent intervention to prevent death *NOTE: this is different than life-threatening serious criteria*.
- Grade 5 (Fatal): Event resulted in death

8.7.7 Causal Relationship of Adverse Events to Investigational Medicinal Products

Medical judgment should be used to determine the cause of the AE considering all relevant factors such as, but not limited to, the underlying study indication, coexisting disease, concomitant medication, relevant history, pattern of the AE, temporal relationship to the study medication, dechallenge or rechallenge. It should be evaluated as to whether or not there is a reasonable possibility that the study drug caused the event.

Not Related (includes events thought to be Unlikely Related)

- An AE that is clearly due to extraneous causes (eg, concurrent disease, concomitant medications, disease under study, etc.)
- It does not follow a reasonable temporal sequence from administration of study drug
- It does not follow a known pattern of response to study drug
- It does not reappear or worsen when study drug is restarted
- An alternative explanation is likely even if not clearly identifiable

Related (includes events thought to be Probably or Possibly Related)

- An AE that is difficult to assign to alternative causes
- It follows a strong or reasonable temporal sequence from administration of study drug
- It could not be reasonably explained by the patient's clinical state, concurrent disease, or other concomitant therapy administered to the patient
- It follows a known response pattern to study drug
- It is confirmed with a positive rechallenge or supporting laboratory data

8.7.8 Outcome and Action Taken

The Investigator will record the action taken and outcome for each AE according to the following criteria:

8.7.8.1 Action Taken with Study Drug

- None
- Dose reduced
- Study drug held/interrupted
- Study drug permanently discontinued
- Not applicable (patient not on study drug at the time of the event)

8.7.8.2 Outcome

- Recovered/Resolved
- Recovered/Resolved with sequelae
- Not recovered/Not resolved
- Death
- Lost to follow-up/Unknown

8.7.9 Follow-up of Adverse Events and Serious Adverse Events

All AEs and SAEs occurring during the study are to be followed up in accordance with good medical practice until resolution or stabilization, until the event returns to baseline status, is determined to be a chronic condition or until patient is lost to follow-up or dies.

8.7.10 Regulatory Aspects of Serious Adverse Event Reporting

8.7.10.1 Investigator and Sponsor Responsibilities

All SAEs, regardless of relationship to study drug, must be reported to the Sponsor within 24 hours of knowledge of the event, according to the procedures below. It is important that the Investigator provide an assessment of relationship of the SAE to study treatment at the time of the initial report. The Novo Nordisk SAE Report Form must be used for reporting SAEs. The contact information for reporting of SAEs can be found on the Novo Nordisk SAE Report Form and Pregnancy Reporting Forms.

The Sponsor or its designee is responsible for submitting reports of AEs associated with the use of the drug that are both serious and unexpected to the United States Food and Drug Administration (FDA), according to 21 Code of Federal Regulations (CFR) 312.32; to the European regulatory authorities according to the European Commission Clinical Trials Directive (2001/20/EC); and to other applicable regulatory authorities, according to national law and/or local regulations.

All Investigators participating in ongoing clinical studies with the study medication will receive copies of these reports for prompt submission to their Institutional Review Board (IRB) or Independent Ethics Committee (IEC). In accordance with the European Commission Clinical Trials Directive (2001/20/EC), the Sponsor or its designee will notify the relevant ethics committees in concerned member states of applicable suspected unexpected serious adverse reactions as individual notifications or through periodic line listings.

8.7.10.2 Sponsor Reporting Timeline

The Sponsor or its designee will submit all safety updates and periodic reports to the regulatory authorities as required by applicable regulatory requirements (ie, within 7 days for treatment related unexpected fatal or life-threatening events; within 15 days for all other treatment related unexpected serious events).

8.7.11 Special Situation Reports

Special situation reports include reports of overdose, medication error, abuse or misuse.

- 1. **Overdose:** Refers to the administration of a quantity of a medicinal product given per administration or cumulatively (accidentally or intentionally), which is above the maximum recommended dose according to the protocol. Clinical judgement should always be applied. In cases of a discrepancy in the drug accountability, overdose will be established only when it is clear that the patient has taken additional dose(s), or the Investigator has reason to suspect that the patient has taken additional dose(s).
- 2. **Misuse:** Refers to situations where the medicinal product is intentionally and inappropriately used in a way that is not in accordance with the protocol instructions or local prescribing information and may be accompanied by harmful physical and/or psychological effects.
- 3. **Abuse:** Is defined as persistent or sporadic, intentional excessive use of a medicinal product, which is accompanied by harmful physical or psychological effects.
- 4. **Medication error:** Is any unintentional error in the prescribing, dispensing, or administration of a medicinal product by a healthcare professional, patient, or consumer, respectively. The administration or consumption of the unassigned treatment and administration of an expired product are always reportable as medication errors, cases of patients missing doses of investigational product are not considered reportable as medication error.

All special situation events as described above must be reported on the Special Situations Report form and faxed/emailed to Novo Nordisk Global Safety (contact information listed below) within 24 hours of knowledge of the event. All AEs associated with these Special Situation events should be reported as AEs or SAEs (as applicable) as well as recorded on the AE eCRF and/or the Novo Nordisk SAE report form. Details of the symptoms and signs, clinical management, and outcome should be provided, when available.

Novo Nordisk Global Safety

[contact]

e-mail: [contact]

9.0 STATISTICAL CONSIDERATIONS

9.1 Statistical Methods

Complete details of the statistical analyses to be performed will be documented in a statistical analysis plan (SAP). This document will include details of analysis populations, summary strategies, analytic approaches, and any amendments to the proposed analyses listed here. Any changes in analyses from those planned in the SAP will be detailed in the final study report.

9.2 Patient Populations for Analysis

- Full Analysis Set (FAS): All patients who signed the informed consent and received at least 1 dose of etavopivat.
- Interim Assessment Set: The first 15 patients overall or first 8 patients per transfusion history stratum in the FAS who completed the Week 24 Response visit and have a baseline record of the primary endpoint.
- Efficacy Evaluable Set: All patients in the FAS who have completed the Week 24 Response visit and who have a baseline record of the primary endpoint.
- Per-Protocol Set (PPS): All patients in the Full Analysis Set who did not have any major protocol violations impacting the efficacy outcomes.
- Safety Set: All patients who received at least one dose of etavopivat.
- Pharmacokinetic Set: All Safety Set patients who have at least one evaluable concentration for etavopivat at a scheduled PK time point after the start of dosing. For patients with protocol violations or events with potential to affect the PK concentrations, a decision regarding inclusion in the analysis will be made on a case-by-case basis.

9.3 Sample Size Considerations

An overall sample size of N=45 will provide 87.3% power to detect an increase in the response rate for the HI-E criteria. Specifically, the assumed response rates are 40% for the etavopivat intervention and 20% otherwise (null-hypothesis comparator). One-sided testing, a significance level of 0.025, and the exact binomial distribution are used for the calculations.

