- All strata (n=15): ≤ 3 responses meeting HI-E criteria, sustained from Week 16 to Week 24.
- Single stratum (n=8): 0 (zero) responses.

If either the overall, or single stratum, futility criterion is met, enrollment may discontinue due to futility. Further enrollment may be considered if it is restricted to specific subsets of patients based on prior transfusion history. If neither criterion is met, enrollment will continue until a total of 45 response-evaluable patients are available at Week 24.

Enrollment will not pause during assessment periods unless futility analysis suggests clinical need to pause.

At final analysis, the study will evaluate the rate of MDS IWG 2018 criteria responses in the pooled, open-label etavopivat-treated patients versus a null-assumed rate of 20%.

Treatment Duration: Duration of study treatment will be up to 48 weeks, including 24 weeks in the Primary Treatment period and 24 weeks in the Extension Treatment period. Patients who demonstrate clinical benefit at 48 weeks of treatment, based on their MDS response assessment, may continue treatment until the patient experiences unacceptable

toxicities, disease progression, withdraws consent, or meets any other discontinuation criteria (Section 7.2.1).

Study Duration: Duration of study for an individual patient is approximately 58 weeks and includes a Screening Period (up to 6 weeks before study treatment), the 24-week Primary Treatment period, the 24-week Extension Treatment period, and Safety Follow-up visit occurring 28 days (+ 7 days) after last dose of study drug. The study duration will be greater than 58 weeks in patients who continue study treatment beyond the planned 48-week treatment period due to clinical benefit.

Number of Participants

Approximately 45 patients will be enrolled.

Key Inclusion Criteria

Type of Participant and Disease Characteristics

- 1. Documented diagnosis of idiopathic/de novo MDS according to World Health Organization (WHO) classification (see Appendix C) that meets the IPSS-R classification (see Appendix B) of very low, low, or intermediate risk disease, and:
 - < 5% blasts and no Auer rods in bone marrow based on local pathology review
 - < Intermediate risk cytogenetic abnormalities per IPSS-R (see Appendix B)
- 2. Anemia defined as:

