9.5 Futility Assessment and Decision Rules

A futility assessment threshold has been selected for this study once 15 patients overall or 8 patients in a single transfusion stratum have evaluable responses on the HI-E criteria at Week 24, whichever occurs first. If the overall futility assessment is performed and \leq 3 responses are observed, enrollment may discontinue for futility. If there are 4 or more responses at 24-weeks observed, enrollment will continue until a total of approximately 45 response evaluable patients are available at Week 24. If the stratum-specific futility assessment is performed and no responses are observed, further enrollment may be restricted to specific subsets of patients based on prior transfusion history.

Enrollment will not pause during assessment periods unless futility analysis suggests clinical need to pause.

Assuming the pooled response rate of 40% is met, the probability of incorrectly declaring futility with 15 evaluable patients is 0.0905. This is calculated using the binomial cumulative distribution function with parameters n=15, p=0.4, x=3.

The single stratum futility assessment allows for the possibility that response rates in a single stratum may be lower than 40%, but the pooled response rate after incorporating the other strata could still reach 40%. The per-stratum futility threshold is intended to terminate enrollment in a stratum where the true response rate can be expected to be <25%. Under a binomial distribution with parameters n=8 and p=0.25, the probability of observing x=0 successes is 0.10011.

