3.11. Futility Assessment

A futility assessment will occur once 15 patients overall or 8 patients in a single transfusion stratum have evaluable responses on the HI-E criteria at W24D1, whichever occurs first.

If the overall futility assessment is performed and ≤ 3 responses are observed, enrollment may discontinue for futility. If there are 4 or more responses at 24-weeks observed, enrollment will continue until a total of approximately 45 response evaluable patients are available at W24D1. A patient with confirmed HI-E response at W16D1 but progression/relapse at W24D1 will be considered a responder for the purposes of the futility assessment.

If the stratum-specific futility assessment is performed and no responses are observed, further enrollment may be restricted to specific subsets of patients based on prior transfusion history.

An informal futility assessment will occur after 15 patients have completed the W24D1 visit or dropped out. The proportion of patients with confirmed HI-E response at any timepoint up to W24D1 will be summarized. Patients discontinuing prior to completing HI-E assessment will be considered non-responders. Additional efficacy and safety data will be summarized for these patients as deemed appropriate.

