4.2.1. Analysis of Primary Endpoints

4.2.1.1. HI-E Response and MDS assessments

The proportion of patients with HI-E response ≥ 8 weeks within 24 weeks of etavopivat treatment will be analyzed across the pooled strata and within each stratum. Patients will be considered responders if they satisfy HI-E criteria during any continuous ≥ 8 -week treatment interval up to W24D1.

HI-E criteria are defined based on the patient's transfusion history stratum at D1:

NTD: A patient is considered a responder where at least one continuous interval ≥ 8 weeks occurs where all of the following criteria are met:

- Hb is increased by ≥ 1.5 g/dL relative to baseline at 2 or more consecutive visits
- Relapse date (date of first Hb measurement with < 1.5 g/dL change from baseline following the qualifying increase) occurs at least 8-weeks after the first incidence of qualifying Hb increase
- Patient is free of RBC transfusions

LTB: A patient is considered a responder if they are free of RBC transfusions over any continuous 8-week period.

HTB: A patient is considered a responder if they have a $\geq 50\%$ reduction in RBC transfusion burden relative to baseline RBC transfusion burden per 8 weeks over any continuous 8-week period.

Percent reduction in RBC transfusion burden is calculated for all rolling 56-day intervals in the 24-week primary treatment period (i.e. Days 2-57, Days 3-58,..., Days 113-168) as

$$-100 \times \frac{RBC \text{ units transfused in 56 day interval} - \text{Baseline RBC transfusion burden per 8 weeks}}{\text{Baseline RBC transfusion burden per 8 weeks}}$$

The numerator for the response rate will be the total number of responders (summed across all baseline transfusion categories). The denominator will be the number of patients in the EES.

MDS baseline assessment including the score based on Revised International Prognostic Scoring System (IPSS-R) for MDS and MDS response assessment will be presented in data listings.

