5. CHANGES FROM PROTOCOL

5.1. Endpoint Phrasing Clarifications

No clarifications need to be made.

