5.2. Changes to Planned Analyses

For the purpose to support an abbreviated CSR, a selected set of endpoints are included in this SAP. The following analysis populations and endpoints mentioned in the protocol are not included:

Protocol Section 3.2:

- The HI-E for \geq 8 weeks within 16 and 48 weeks of etavopivat
- The HI-E for \geq 16 weeks within 24 and 48 weeks of etavopivat
- Overall response rate (2006 International Working Group [IWG] Criteria) (see protocol Appendix A)
- Duration of response (2006 IWG Criteria)
- Increase in neutrophils and/or platelets counts
- Decrease in ferritin and transferrin saturation (TSAT)
- Decrease in iron chelation therapy
- Overall survival

Protocol Section 3.3:

- PK: maximum observed plasma concentration, time to maximum observed plasma concentration, area under the plasma concentration-time curve from time zero until the last quantifiable time point (AUC0-last), from time zero to infinity (AUC0-inf), for a dosing interval (AUCtau/AUC0-24).
- RBC 2,3-DPG and ATP levels over time

Protocol Section 3.4:

- Change from baseline in Patient-Reported Outcome Measurement Information System (PROMIS) Fatigue Scale at Weeks 16, 24, and 48
- Change from baseline in The Quality of Life in Myelodysplasia Scale (QUALMS) patient-reported outcome assessment at Weeks 16, 24, and 48
- Cell colony analysis of bone marrow progenitors
- Cytomorphology (blast, M/E, and ringed sideroblast determination) and cytogenetics of bone marrow
- Markers of ineffective erythropoiesis and iron metabolism
- Cancer-associated mutations and/or genetic alterations in responding and non-responding patients
- Flow cytometry analysis of terminal erythroid differentiation

Protocol Section 9.2:

- Interim Assessment Set and Per-Protocol Set

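### The stated 87.3% power is not the exact-binomial figure it is said to be (that is 85.7% at N=45), and the overall futility responder is defined in two conflicting ways

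*Protocol*

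**What the plan says.** **Power.** Protocol 9.3 states: "An overall sample size of N=45 will provide 87.3% power to detect an increase in the response rate for the HI-E criteria". The assumed rates are 40% on etavopivat and 20% under the null, and the method is named: "One-sided testing, a significance level of 0.025, and the exact binomial distribution are used for the calculations". SAP 3.1 repeats both sentences. Protocol 9.6.1 plans a one-sided exact binomial test at 0.025 for the final analysis. Neither document states the number of responders needed for success.

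**Futility responder.** The overall rule looks at 15 patients and is met at 3 or fewer responses. The response counted is described differently in different places:

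- Protocol 1.1, Protocol 4.1 and SAP 1.2.1 count "responses meeting HI-E criteria, sustained from Week 16 to Week 24".
- Protocol 9.5 gives the same threshold without that condition.
- SAP 3.11 says: "A patient with confirmed HI-E response at W16D1 but progression/relapse at W24D1 will be considered a responder for the purposes of the futility assessment".

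**Related text.** Protocol 9.5 and SAP 3.11.1 both state that, at a pooled rate of 40%, "the probability of incorrectly declaring futility with 15 evaluable patients is 0.0905". For the primary endpoint, SAP 4.2.1.1 says: "Patients will be considered responders if they satisfy HI-E criteria during any continuous" interval of at least 8 weeks up to W24D1. On endpoint wording, SAP 5.1 says "No clarifications need to be made". SAP 5.2 lists "Interim Assessment Set and Per-Protocol Set" among the items dropped and does not mention the futility responder.

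**The concern.** The inputs in Protocol 9.3 determine the exact power completely, so the printed figure can be checked, and it does not agree with the method it cites. The SAP that supports the abbreviated clinical study report carries the same sentence.

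The futility texts classify the same patient differently. Someone with a confirmed Week 16 response that is lost by Week 24 is a non-responder under the synopsis wording and a responder under SAP 3.11. The conflict lies inside the SAP as well as between the SAP and the protocol. The threshold is a small integer, so a single patient can decide whether the criterion is met, and a report of the futility result would have two definitions to choose from. The 0.0905 operating characteristic is also tied to a response rate without a clear statement of which response is meant.

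**Working it through.** **Inputs.** N = 45, null rate 0.20, alternative 0.40, one-sided alpha 0.025, exact binomial (Protocol 9.3, SAP 3.1). Futility: n = 15, stop threshold 3, rate 0.40 (Protocol 9.5, SAP 3.11.1). Visit days: Week 16 Day 1 = Day 106 and Week 24 Day 1 = Day 162 (SAP Table 3). The sample size needs no dropout adjustment, because SAP 3.8 allows replacement to reach 45 evaluable patients.

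**1. Exact power.** The test rejects at the smallest r for which P(X ≥ r | 45, 0.20) ≤ 0.025. Power is P(X ≥ r | 45, 0.40).

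| Cutoff r | Attained alpha | Power |
|---|---|---|
| 14 | 0.05207 | 0.9164 |
| **15** | **0.02499** | **0.8570** |
| 16 | 0.01100 | 0.7751 |

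The rule is 15 or more of 45, with 85.7% power. The neighbouring cutoffs give 91.6% (with alpha above 0.05) and 77.5%. None gives 87.3%.

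**2. Where 87.3% may come from.** Three approximations at one-sided 0.025:

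- Normal, null variance in the critical value, no continuity correction: Φ((0.20 − 1.96·√(0.16/45)) / √(0.24/45)) = Φ((0.20 − 1.96 × 0.05963) / 0.07303) = Φ(1.138) = 0.8725.
- The same with continuity correction (subtract 1/90 in the numerator): 0.8380.
- Arcsine: Φ(2·√45·(asin√0.4 − asin√0.2) − 1.96) = 0.8428.

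Only the first rounds to 87.3%. That origin is an inference; the mismatch with the named method is not.

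**3. The plan's futility figure.** P(X ≤ 3 | 15, 0.40) = 0.0005 + 0.0047 + 0.0219 + 0.0634 = 0.0905. The arithmetic in Protocol 9.5 and SAP 3.11.1 is right.

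**4. Effect of the two responder definitions on the count.** Take 15 patients of whom 3 hold a response from Week 16 through Week 24, 1 responded at Week 16 and relapsed by Week 24, and 11 never responded.

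- Synopsis wording: 3 responses, at or below 3, criterion met.
- SAP 3.11 wording: 3 + 1 = 4 responses, enrolment continues.

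**5. Effect on 0.0905.** Week 16 to Week 24 spans 162 − 106 = 56 days, or 8 weeks. A response held over that span lies inside the primary definition (any continuous interval of at least 8 weeks up to W24D1). The same is true if the wording means that HI-E was already met at Week 16 and was then kept. The sustained rate therefore cannot exceed the primary rate. P(X ≤ 3) rises as the rate falls, so if the primary rate is 40% the wrong-stop probability under the sustained definition is at least 0.0905. The documents give no sustained rate. With assumed rates, for illustration only:

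| Rate of the counted response | P(X ≤ 3 of 15) |
|---|---|
| 0.40 (plan) | 0.0905 |
| 0.39 (assumed) | 0.1039 |
| 0.35 (assumed) | 0.1727 |

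**6. Context.** The 85.7% ignores the futility look, which is non-binding. If the 3-of-15 rule were binding and counted the same response as the final test (both assumptions), power would be 81.0% and alpha 0.022.

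**The case against.** The power gap is small: 87.3 − 85.7 = 1.6 points, with power above 80% either way and no change to N, alpha or the test. The SAP was written after early termination, and SAP 4.2.1.1 describes a response rate without a hypothesis test, so SAP 3.1 now drives nothing. This stands. Taken alone, the power half is a correction of record.

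On futility, crossing the threshold does not force a stop. At 3 or fewer responses enrolment may be discontinued, or may be restricted to subsets. That also stands, and it softens the consequence. But 4 or more means enrolment will continue, so the count still decides whether the discretion to stop arises at all.

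The detailed sections can be read as settling the matter. Protocol 9.5 has no sustained condition, and Protocol 9.1 leaves the details to the SAP. SAP 3.11 also adds an informal assessment that counts a confirmed response at any time up to W24D1, with early discontinuers as non-responders. This makes the SAP 3.11 reading plausible as the intended one. It does not remove the conflict: SAP 1.2.1 still carries the stricter wording, and SAP section 5 lists no change, although SAP 1.1 says differences from the protocol will be outlined. The informal count also uses completers plus dropouts rather than 15 evaluable patients, which is a further reason to state one definition.

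Two more points have partial force. The 40% in the 0.0905 statement is most naturally the primary HI-E rate, but the stricter futility wording prevents that from being certain. SAP section 4 lists no formal futility output, so the issue arises only if the report describes the futility result.

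**Conclusion.** Both parts hold. The exact power at N=45 is 85.7%, with success at 15 or more of 45 and attained alpha 0.02499. The stated 87.3% is 1.6 points too high for the named method. This follows entirely from the plan's own inputs. Its practical weight is small.

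The futility-responder conflict is real and undeclared, and it is the reason the point should be acted on. One relapsed Week 16 responder can move the count from 3 to 4 of 15 and so change whether the criterion is met. The 0.0905 is correct at a 40% rate for whatever response is counted. If 40% is the primary rate, 0.0905 is a lower bound under the sustained definition; how far above it the true value lies depends on a sustained rate that the documents do not give.

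**What to change.** 1. In Protocol 9.3 and SAP 3.1, replace the power sentence with: *N=45 evaluable patients; success is 15 or more responders of 45; exact one-sided alpha 0.02499; exact power 85.7% at a 40% response rate, not accounting for the non-binding futility assessment.*
2. Reconcile Protocol 1.1, 4.1 and 9.5 with SAP 1.2.1 and 3.11, including the informal assessment in 3.11, to one futility-responder definition and one denominator. The sponsor must choose the definition. If SAP 3.11 is kept, list it in SAP section 5 as a change from the protocol.
3. Beside 0.0905, state which response has the assumed 40% rate. The figure stands if that is the response counted. If the sustained definition is kept, recompute the figure at an explicitly assumed sustained rate.

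The cost is wording only: N, test, alpha and data collection are untouched. The stated power becomes slightly less favourable, and the sponsor is committed to one futility count. Since the study ended early, if a protocol amendment with ethics committee approval is judged disproportionate, a SAP section 5 entry and a note in the clinical study report would put the same corrections on record.
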